5.6.1 Treatment Regimen/Dosage Adjustments/Dose Discontinuation

If the study eye develops a treatment-related adverse event at any time during the study, treatment dose may be temporarily held or discontinued and the reason for dose holding or discontinuation will be recorded on the eCRF.

The treatment regimen will be adjusted based on the following criteria:

- Intraocular inflammation: discontinue the dose and exit the patient when the event of intraocular inflammation has been resolved. For more information, refer to Section 6.3.2.
- IOP: hold dose if IOP is ≥ 30 mm Hg in the study eye. Treatment may resume when IOP is < 30 mm Hg, either spontaneously or by treatment, as determined by the evaluating physician.
- New retinal break or retinal detachment: hold dose for the study eye. Treatment may resume after the retinal break/detachment has been successfully treated.
- Ocular and/or periocular infection: hold dose until the infection is resolved in both eyes

The investigator may hold or discontinue study treatment for other safety reasons at his/her discretion.

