9.1 Definitions

9.1.1 Adverse Event

An adverse event is any untoward medical occurrence in a patient or clinical investigation patient administered a pharmaceutical product and that does not necessarily have a causal relationship with this treatment. An adverse event can therefore be any unfavorable and unintended sign (including an abnormal laboratory finding), symptom, or disease temporally associated with the use of a medicinal (investigational) product, whether or not related to the medicinal (investigational) product. In addition, during the screening period, adverse events will be assessed regardless of the administration of a pharmaceutical product.

Note: Adverse events must be collected once informed consent has been obtained, regardless of whether or not the patient has been administered study drug.

Progression of treatment indication including new or worsening of anticipated clinical signs or symptoms, which are collected as clinical efficacy variables and assessed as unequivocally associated with the disease progression and/or lack of efficacy, should NOT be reported as

adverse events unless the disease progression is greater than anticipated in the natural course of the disease.

Adverse events will be assessed, documented, and recorded in the eCRF throughout the study (ie, after informed consent has been obtained). At each visit, the investigator will begin by querying for adverse events by asking each patient a general, non-directed question such as “How have you been feeling since the last visit?” Directed questioning and examination will then be done as appropriate. All reported adverse events will be documented on the appropriate eCRF.

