2.3 Data Conventions

Unless stated otherwise in specific subsequent sections, data conventions and definitions listed below will be applied to all analyses.

- Day 1 is defined as the day when the patient receives the 1st study treatment Study days = visit date – date of the 1st study treatment + 1
- Study duration for the final DBL = date of the Week 28 visit (or early exit) date of the 1st study treatment + 1
- Unless otherwise specified, baseline data refer to assessments performed at Baseline (Day 1) visit prior to the 1st study treatment. Screening or unscheduled visits prior to Baseline (Day 1) visit will be used for baseline in the absence of pertinent data at the Baseline (Day 1) visit
- Data collected after the 1st administration of any non-study (concomitant/prohibited) ocular anti-VEGF treatment in the study eye will be excluded from all efficacy analyses
- When AE date is partial or missing, the following missing data imputation will be used
 - If AE start date is missing, the start date will be assigned to the 1st day of the month if the day of the month is missing or to January if the month of the year is missing

- If AE stop date is missing, the stop date will be assigned to the last day of the month if the day of the month is missing or to December if the month of the year is missing
- Descriptive statistics include the sample size (N), mean, standard deviation (SD), median, minimum (Min), and maximum (Max) for continuous/ordinal data and the frequency distribution includes sample size (N), frequency count, and percentage for categorical data
- Medical Dictionary of Regulatory Activities (MedDRA) nomenclature will be used to code adverse events, medical procedures, biomicroscopy, and ophthalmoscopy findings
- The Anatomical-Therapeutic-Chemical classification text from World Health Organization (WHO) Drug Dictionary will be used to code all medications for drug class and for drug name
- Whenever applicable, metric systems will be used (eg, kilograms [kg] and centimeters [cm]) and all clinical laboratory data will be presented with the Standard International (SI) units

3. Disposition, Exit Status, and Significant Protocol Deviations

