3.1 Disposition and Exit Status

Patient disposition will be summarized as a frequency distribution using the safety population. For Week 12 analysis, patients who are still in the study will be classified into "ongoing" category. Reasons for early exit will be summarized into the following categories as captured on the study exit eCRF:

- Screen Failure
- Adverse Event
- Withdrawal by subject
- Lost to Follow-Up
- Pregnancy
- Death
- Physician decision
- Progressive disease

- Protocol Deviation
- Study Terminated by the Sponsor
- Site Terminated by the Sponsor
- Other

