6.2 Adverse Events

A treatment-emergent adverse event (TEAE) is an adverse event that occurs after the initiation of the study treatment (ie, the onset date is the same as or after the first study treatment date), or an adverse event with onset prior to the study treatment that worsened in severity or became serious after the initiation of the study treatment. The incidence of

TEAEs will be calculated and presented as the number and percent of patients experiencing the TEAE during the reporting period.

The following summaries of TEAE data will be performed: 1) overall summary, 2) all TEAEs regardless of causality, 3) treatment-related TEAEs, 4) ocular TEAEs in the study eye, 5) non-ocular TEAEs, 6) treatment-related ocular TEAEs, and 7) TEAEs of special interest. An additional summary will be provided for 8) treatment-emergent serious adverse events (TE SAEs) and 9) AEs leading to study discontinuation.

[figure not shown]
The overall summary will present the data by the number and percent of patients with TEAEs, ocular/non-ocular TEAEs, treatment-related ocular/non-ocular TEAEs, AEs leading to study discontinuation, TE SAEs, and death. Treatment-related ocular TEAEs will also be summarized for procedure-related and drug-related TEAEs. Procedure-related TEAEs are those TEAEs marked as related to the "Study Procedure" and drug-related TEAEs are those marked as related to the "Study Drug".

[figure not shown]
Further, tabulations of TEAEs or TE SAEs based on MedDRA coded terms, primary system organ class (SOC) and/or preferred terms (PTs), will be sorted by the frequency of occurrence as detailed below.

Summary for 3) treatment-related TEAEs, 5) non-ocular TEAEs, 8) TE SAEs, and 9) AEs leading to study discontinuation will be sorted by primary SOC in alphabetical order. Within each SOC name, TEAEs (TE SAEs or AEs) will be tabulated by PT in descending order. A patient with multiple occurrences of the same PT within the reporting period will be counted only once for that PT.

Summary for 2) TEAEs by severity will be sorted by primary SOC in alphabetical order and by the worst severity (maximum severity) experienced for a given patient. Within each SOC, TEAEs will be tabulated by PT in descending order and by severity. The severity of a TEAE is defined as the greater of the onset severity and maximum severity recorded on the CRF for each unique PT reported by the patient.

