Summary for 4) ocular TEAEs, 6) treatment-related ocular TEAEs, and 7) TEAEs of special interest of intraocular inflammation will be sorted by preferred term in descending order. A patient with multiple occurrences of the same preferred term within the reporting period will be counted only once for that PT.

7. Interim Analyses

An interim analysis (IA) is planned when all patients have completed the Week 12 visit or have exited early from the study.

A data summary will be presented for all available cumulative data by focusing on safety especially intraocular inflammation AE rates.

8. Deviations from Protocol

This is the original analysis plan and there are no deviations from the current study protocol.

9. References

SAS/STAT User's Guide Version 9.3, SAS Institute Inc., Cary, NC

10. Amendment(s)

None.

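### Partial AE onset dates are imputed without reference to the first injection, so an early post-injection event can be dated before treatment and drop out of the TEAE tables

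*SAP*

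**What the plan says.** SAP 2.3 (Data Conventions) gives the rule for partial AE onset dates: "If AE start date is missing, the start date will be assigned to the 1st day of the month" if only the day is unknown, and to January if the month is unknown. The conventions in that section apply to every analysis unless a later section overrides them. The rule does not mention the date of first treatment. It also gives no instruction for an onset whose year is missing, although its lead-in covers missing dates as well as partial ones.

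SAP 6.2 (Adverse Events) defines a TEAE in two ways. The first is by date: "the onset date is the same as or after the first study treatment date". The second admits an event with earlier onset that "worsened in severity or became serious after the initiation of the study treatment". The visible text of Section 6.2 has no separate rule for partial dates.

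The TEAE tables built on this definition include "6) treatment-related ocular TEAEs, and 7) TEAEs of special interest". The last of these covers intraocular inflammation: "7) TEAEs of special interest of intraocular inflammation will be sorted by preferred term in descending order".

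Protocol 9.1.1 states that "Adverse events must be collected once informed consent has been obtained", so AEs with a genuine pre-injection onset are expected in the database.

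**The concern.** The two SAP rules combine badly. The imputation always moves a partial onset to the earliest date it could be, and the TEAE definition then treats that date as real. Take an assumed first injection on 10 September 2018 and a true onset on 14 September 2018. If the day is not recorded, onset becomes 1 September. If the month is not recorded either, onset becomes 1 January 2018. Both precede the injection, so the event is not a TEAE unless it later worsens or becomes serious.

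Because AEs are collected from consent, a date before the injection would not stand out as a data error. The date test also takes no account of the investigator's causality assessment, so an event marked as related to drug or procedure could leave the treatment-related tables.

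Safety is part of the primary objective. Compared with a rule that refers to the first dose, the current rule can only lower TEAE counts. With about 100 patients, each patient whose only event of a given type is lost lowers that incidence by about 1/100, or 1 percentage point.

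**Working it through.** The plan gives no figure to reproduce. The check applies SAP 2.3 and 6.2 to every combination of first-dose date and onset day.

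**Inputs.** The imputation rule is from SAP 2.3, the TEAE date test from SAP 6.2, and the study length of 28 weeks = 196 days from SAP 1.1. Assumptions, not in the documents: first dose uniform over a 365-day year, true onset uniform over days 0 to 195 after it, and missingness unrelated to onset time.

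**Day missing, whole study.** An onset is misdated when it falls in the dosing month and dosing was not on the 1st. For a month of L days and dosing day d (2 to L), the onset days left in that month number L − d + 1. Summed over d this is L(L − 1)/2.
- Seven 31-day months: 7 × 465 = 3,255
- Four 30-day months: 4 × 435 = 1,740
- February: 378
- Total misdated: 5,373
- Combinations: 365 × 196 = 71,540
- Share: 5,373 / 71,540 = **7.51%**, about 0.75 per 10 such AEs

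**Where the loss falls.** Only 25 of the 5,373 have onset after day 27.
- Days 0–27: 5,348 / (365 × 28) = 5,348 / 10,220 = **52.33%**
- Days 28–195: 25 / (365 × 168) = 25 / 61,320 = **0.04%**
- Days 0–83, the span to the Week 12 interim: 5,373 / (365 × 84) = 5,373 / 30,660 = **17.5%**

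**If missingness depends on timing.** Let r be the chance of a missing day for onsets in days 0–27 relative to later onsets. The 28-week share is (5,348r + 25) / (10,220r + 61,320).

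| r | Share misdated over 28 weeks |
|---|---|
| 0.1 | 0.90% |
| 0.25 | 2.13% |
| 0.5 | 4.06% |
| 1 | 7.51% |
| 2 | 13.11% |

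That is about 0.1 to 1.3 lost per 10 post-injection AEs with a missing day.

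**By dosing day, onsets in days 0–27.** 0% if dosed on the 1st, 99.7% on the 2nd, 58.6% on the 15th, 12.2% on the 28th.

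**Year-only dates, days 0–195.** Every onset in the dosing year is misdated unless dosing was on 1 January. The share is 100% for dosing from 2 January to 19 June, 108/196 = 55.1% on 15 September and 17/196 = 8.7% on 15 December. With AEs queried at every visit, such dates are likely to be rare.

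**With a first-dose reference rule.** None of the 71,540 day-missing post-injection combinations is dated before treatment. The cost lies in screening AEs. A true screening onset j days before dosing, with the day missing, would count as a TEAE if it fell in the dosing month. For a screening period of w days the share is the average of min(d − 1, w)/w over all dosing days.
- w = 2: 694/730 = 95.1%
- w = 21: 4,893/7,665 = 63.8%

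Under the current rule that share is 0%. These figures assume onset uniform over screening and no earlier stop date.

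**The case against.** The strongest reply is that this is a convention, not an error. The rule is explicit and reproducible. A month-only date in the dosing month is ambiguous, and no rule recovers the truth. The alternative moves the misclassification to screening AEs, and the documents do not show that it would misclassify fewer events overall. This stands in part: the choice is one of direction. For a safety objective, however, the usual preference is to err towards counting.

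SAP 4.3 does not show an internal inconsistency. Its medication algorithm compares year and month first but then falls back on the same dates, and it gave the same result as SAP 2.3 in all 158,410 combinations tried (217 days × 365 dosing dates × 2 types of partial date).

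The second reply is that the effect is unshown and other data would catch what matters. No partial-date rate is given. Protocol 9.1.1 has AEs queried at every visit, Protocol 10.4.1 puts the injection date in source, and Protocol 9.3 requires SAE reports within 24 hours. The study is single-arm and descriptive, and no visible decision rule uses a TEAE count. If the database refuses partial dates or they are all queried to resolution, the effect is nil.

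Intraocular inflammation has further protection. Protocol 5.6.1 says to "discontinue the dose and exit the patient when the event of intraocular inflammation has been resolved", so these patients should appear in disposition ("Reasons for early exit will be summarized into the following categories as captured on the study exit eCRF") and in the summary of AEs that led to discontinuation, which is not worded as limited to TEAEs. Biomicroscopy, ophthalmoscopy and post-injection assessments are also separate safety variables in SAP Section 6.

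All of that stands and keeps the point minor. None of it returns a misdated event to the TEAE tables. An event that neither causes exit nor worsens nor becomes serious appears in no other AE summary listed in SAP 6.2. Because exit follows resolution, a patient with unresolved inflammation at the Week 12 cut could still be classed as ongoing. The SAP does not say whether the interim inflammation rates are restricted to TEAEs.

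**Conclusion.** The concern holds, as a minor point. On the visible text the mechanism is certain: a post-injection AE with a partial onset in the month or year of first dosing is classified as pre-treatment, apart from the exceptions for dosing on the 1st (or 1 January) and for later worsening or seriousness. The loss falls almost entirely on events in the first four weeks after the first injection.

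The size is conditional on a partial date existing. The 7.5% central figure and the 0.9% to 13.1% range rest on uniform dosing and onset dates and on assumed missingness patterns. The number of AEs they apply to is unknown and probably small. The missing-year gap is real, but its effect cannot be estimated.

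**What to change.** Add to SAP 2.3 or 6.2:
- If the known part of the onset date (month and year, or year alone) equals that of the first study treatment, impute the first treatment date, unless a recorded stop date shows that the event ended earlier. Otherwise keep the current rule.
- If the onset date is completely missing, treat the event as treatment-emergent unless the stop date precedes first treatment.
- List all AEs whose TEAE status depends on imputation.

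The cost is a short addition to the SAP, about one line of derivation code and a short listing. The downside is that some screening AEs with a missing day would count as TEAEs (the 64% to 95% computed above), which is conservative for safety. If the sponsor prefers to keep the current rule, the listing alone would show how many events are affected and has no such downside.

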3.1 Disposition and Exit Status

Patient disposition will be summarized as a frequency distribution using the safety population. For Week 12 analysis, patients who are still in the study will be classified into "ongoing" category. Reasons for early exit will be summarized into the following categories as captured on the study exit eCRF:

- Screen Failure
- Adverse Event
- Withdrawal by subject
- Lost to Follow-Up
- Pregnancy
- Death
- Physician decision
- Progressive disease

- Protocol Deviation
- Study Terminated by the Sponsor
- Site Terminated by the Sponsor
- Other

3.2 Significant Protocol Deviations

Significant protocol deviations will be classified based on the type of deviations. Summary of significant protocol deviations will be done for the safety population.

4. Demographics and Other Baseline Characteristics

4.1 Demographics

Demographic data are collected at the screening visit. Patient's age (years), sex, and race will be summarized. Patient age will be classified into categories of less than or equal to 65 years, and greater than 65 years.

4.2 Baseline Characteristics

Baseline characteristics include height (cm), weight (kg), BMI (kg/m²), iris color, subretinal or intraretinal fluid, intraretinal cysts, pigment epithelial detachments, and smoking status. Ocular characteristics of the study eye at baseline include lens status, study eye as the better-seeing eye (defined as baseline $BCVA_{study-eye} > BCVA_{non-study eye}$), BCVA, CRT, and intraocular pressure. Baseline characteristics will be summarized using descriptive statistics.

4.3 **Prior Medications/Procedures**

Prior medications are defined as those received prior to the first study treatment. For analysis purposes, a medication will be considered as prior medication if it satisfies at least one of the following:

- The start date is prior to Baseline (Day 1), regardless of the stop date;
- The start date is unknown but marked as > 1 year; or
- The stop date is prior to or on Baseline (Day 1), regardless of the start date

For medications with a partial start or stop date where "> 1 year" is not marked for the start date or "ongoing" is not marked for the stop date and the day and/or the month is unknown, comparison to the 1^{st} study treatment date, Baseline (Day 1), will start with the year followed by the month, if applicable, for determination of prior medications. In cases where a full determination cannot be made based on the partial information, the start date will be assigned

to the 1st day of the month if the day of the month is missing or to January if the month of the year is missing; conversely, the stop date will be assigned to the last day of the month if the day of the month is missing or to December if the month is missing. This missing data imputation will only be used to determine whether certain medication is considered as prior medication.

Prior medications will be summarized under each drug class and drug name. A separate analysis for prior ophthalmic medications used in the study eye will be performed based on WHODDE base preferred names.

In addition, ocular anti-VEGF treatment history will be summarized with two categories, treatment-naïve and treatment-experienced. Ocular anti-VEGF treatment includes the following anti-VEGF injections ranibizumab, bevacizumab, pegaptanib, and aflibercept or treatment with a systemic anti-VEGF agent including bevacizumab, and ziv-aflibercept or VEGF-receptor inhibitor such as sunitinib, sorafenib, and pazopanib.

4.4 Concomitant Medications/Procedures

Concomitant medications are defined as those non-study medications received but after the first study treatment. For analysis purposes, a medication will be considered as concomitant if it satisfies at least one of the following:

- The start date is on or after the first treatment date regardless of the stop date;
- The stop date is after the first treatment date, regardless of the start date; or
- The stop date is unknown but marked as ongoing

For medications with a partial start or stop date, the same conventions and algorithms as described for prior medications will be used for determination of concomitant medications.

Concomitant medications will be summarized in the same way as prior medications.

Concurrent procedures including those ocular and non-ocular procedures performed after study treatment will be coded using MedDRA dictionary. The number and percent of patients with any concurrent procedures will be tabulated and presented as a frequency distribution for each primary SOC and preferred term. A separate summary for ocular concurrent procedures in the study eye will be performed.

4.5 Medical History

Medical history will be coded using MedDRA dictionary.

Data will be summarized by frequency distribution for each unique primary SOC and preferred terms based on the following two categories:

- Previous Medical Conditions, and
- Medical Conditions at Trial Initiation

Further, ocular history for the study eye will be summarized similarly.

5. Efficacy Assessments and Analyses

Efficacy assessments include BCVA and CRT measured in the study eye.

5.1 Efficacy Assessments

5.1.1 Best-Corrected Visual Acuity (BCVA)

Best-corrected visual acuity (BCVA) will be recorded on the CRF as the number of letters correctly read using the Early Treatment of Diabetic Retinopathy Study (ETDRS) letters (Age-Related Eye Disease Study [AREDS] Research Group, 2001). For a given eye, the 4 meter distance (standard) of BCVA is tested first. If the patient correctly reads at least 20 letters at 4 meters, BCVA score will be set as the sum of 30 and the number of letters read correctly. If the patient correctly reads less than 20 letters at 4 meters, the BCVA is measured again at 1 meter. The BCVA score will be set to the number of letters read correctly at 1 meter plus the number of letters read correctly at 4 meters.

For each patient, BCVA data will be collected for both eyes at the screening, baseline visit (Day 1 but prior to the study treatment), and at 28/early exit visits; and for the study eye only at Weeks 4, 8, 12, 16, 20, and 24.

